Appendix 5. Hepatic Monitoring Tests for Treatment-Emergent Abnormality

Selected tests may be obtained in the event of a treatment-emergent hepatic abnormality and may be required in follow-up with patients in consultation with the Lilly clinical research physician.

Hepatic Monitoring Tests

Hepatic Hematology^a

Hemoglobin (HGB)
 Hematocrit (HCT)
 Erythrocytes (RBC)
 Leukocytes (WBC)
 Neutrophils^b
 Lymphocytes
 Monocytes
 Eosinophils
 Basophils
 Platelets (PLT)

Hepatic Chemistry^a

Total bilirubin
 Direct bilirubin
 Alkaline phosphatase
 Alanine aminotransferase (ALT)
 Aspartate aminotransferase (AST)
 Gamma-glutamyl transferase (GGT)
 Creatine phosphokinase (CPK)

Haptoglobin^a

Hepatic Coagulation^a

Prothrombin time (PT)
 Prothrombin time, INR

Hepatic Serologies^{a,c}

Hepatitis A antibody, total
 Hepatitis A antibody, IgM
 Hepatitis B surface antigen
 Hepatitis B surface antibody
 Hepatitis B Core antibody
 Hepatitis C antibody
 Hepatitis E antibody, IgG
 Hepatitis E antibody, IgM

Recommended Autoimmune Serology^a

Anti-nuclear antibody
 Anti-smooth muscle antibody
 Anti-actin antibody

Abbreviations: CRF = case report form; IgG = immunoglobulin G; IgM = immunoglobulin M; INR = international normalized ratio; RBC = red blood cells; WBC = white blood cells.

^a Assayed by Lilly-designated laboratory.

^b Neutrophils reported by automated differential hematology instruments include both segmented and band forms. Whenever a manual differential is needed to report the neutrophils, the segmented and band forms should be added together and recorded on the CRF, unless the CRF specifically provides an entry field for bands.

^c Reflex/confirmation dependent on regulatory requirements and/or testing availability.

Appendix 6. Creatinine Clearance Formula

Note: This formula is to be used for calculating creatinine clearance (CrCl) from **local laboratory results only**.

Cockcroft-Gault prediction of creatinine clearance from serum creatinine (1976)

For serum creatinine concentration in mg/dL:

$$\text{CrCl} = \frac{(140 - \text{age}^a) \times (\text{wt}) \times 0.85 \text{ (if female), or } \times 1.0 \text{ (if male)}}{72 \times \text{serum creatinine (mg/dL)}} \text{ (mL/min)}$$

For serum creatinine concentration in $\mu\text{mol/L}$:

$$\text{CrCl} = \frac{(140 - \text{age}^a) \times (\text{wt}) \times 0.85 \text{ (if female), or } \times 1.0 \text{ (if male)}}{0.81 \times \text{serum creatinine } (\mu\text{mol/L})} \text{ (mL/min)}$$

^a Age in years, weight (wt) in kilograms.

Source: Cockcroft and Gault 1976.

Appendix 7. Protocol Amendment I4D-MC-JTJN(b) Summary

A Phase 2 Study of Prexasertib in Platinum-Resistant or Refractory Recurrent Ovarian Cancer

Overview

Protocol I4D-MC-JTJN (A Phase 2 Study of Prexasertib in Platinum-Resistant or Refractory Recurrent Ovarian Cancer) has been amended. The new protocol is indicated by amendment (b) and will be used to conduct the study in place of any preceding version of the protocol.

The overall changes and rationale for the changes made to this protocol are as follows:

- Section 2 Table JTJN.1. Schedule of Inclusion and Baseline Assessments: clarified that Cohort 4 does not need local *BRCA* results
- Section 2 Post-Study Treatment Follow-Up Schedule of Activities: differentiated follow-up intervals for patients who have discontinued without progression versus with progression
- Section 6.1 Inclusion Criteria: inclusion [3] clarifies what is considered as a line of therapy
- Section 7.4 Table JTJN.7: included Grade 2 for consideration in thrombocytopenia; specified when treatment should be delayed for anemia
- Section 10.2: included definition for per-protocol population
- Section 10.3: modified when to conduct primary analysis and additional updated analyses of efficacy and safety, based on a recommendation from the FDA
- Section 10.3.3.4 Extent of Exposure: clarified definition with additional criteria
- Section 10.3.4 Interim Analyses: defined threshold of activity for each cohort

Revised Protocol Sections

Note: Deletions have been identified by strike throughs. Additions have been identified by the use of underline .

The numbering system used for inclusion and exclusion criteria provides a unique number for each criterion and allows for efficiency in data collection.

In case an amendment to the protocol adds a criterion, that criterion will receive the next available number, regardless of whether it is an inclusion or exclusion criterion.

Table JTJN.11. Schedule of Inclusion and Baseline Assessments

Procedure Category	Procedure				Comments
Study Entry/ Enrollment	...				
	Cohorts 1-3: Confirm availability of local BRCA result		X		Data from a blood or tissue based test are acceptable (i.e., either germline or somatic tests are acceptable). The test may have occurred prior to consent. If both somatic and germline status are known, the somatic status should be used for cohort assignment. Patients in Cohort 4 do not need to have local BRCA results.

Post-Study-Treatment Follow-Up Schedule of Activities

...

- a Period begins the day after the decision that the patient will discontinue study treatment is made and lasts approximately 30 days.
- b For patients who have discontinued without progression, follow-up should occur every 60 days. For patients with progression, the follow-up interval is 90 days for survival assessments. Period begins 1 day after short-term follow-up period is completed and continues until death, study withdrawal, or the patient is lost to follow-up.

6.1 Inclusion Criteria

[3] ...

Note for Cohorts 1 and 2: Each line of therapy is preceded by evidence of clinical or radiographic disease progression (initial therapy is considered the first line). Switch of an agent within the same drug class (for example, cisplatin to carboplatin) within a regimen to manage toxicity does not define the start of a new line of therapy. Similarly, maintenance therapy (continuation maintenance or switch maintenance) will not be considered a new line of treatment. ~~Neither adjuvant therapy nor hormonal therapy are considered lines of therapy.~~ Hormonal therapy is not considered a line of therapy. All adjuvant therapy should be considered as a line of therapy.

Table JTJN.12. Dose Adjustments and Delays

Toxicity	CTCAE Grade	Action	Dose Adjustments and Considerations
...			
Thrombocytopenia	Grades 2, 3 or Grade 4	Delay treatment until \leq Grade 1 ($\geq 75/\text{mm}^3$)	Investigator discretion
Anemia	Grade 3 or Grade 4	Consider RBC transfusion or EPO (if consistent with institutional guidelines). Treatment may proceed or be delayed at the discretion of the investigator. Delay treatment until $<$ Grade 2 ($\geq 8 \text{ g/dL}$)	Investigator discretion
...			

10.2. Populations for Analyses

The following analysis sets will be defined for this study:

...

Per-Protocol population: will include all treated patients who do not have any major protocol violations that could potentially affect the efficacy conclusions of the study. This population will be used for efficacy and PRO sensitivity analyses.

10.3. Statistical Analyses

Statistical analysis of this study will be the responsibility of Lilly or its designee.

The primary analysis ~~of the primary endpoint of ORR will be performed when all enrolled patients have completed ≥ 2 months of follow-up and/or investigator-assessed best response assessments have been completed for all patients.~~ All secondary endpoints will be evaluated at this time. will be conducted approximately 6 months after the last responder's first response date or approximately 1 year after the last patient has been enrolled, whichever occurs first.

Additional updated analyses of efficacy and safety may be conducted at later times (approximately ~~10-18~~ 6-12 months after last patient is enrolled the primary analysis) if deemed appropriate by the sponsor.

10.3.3.4 Extent of Exposure

The number of cycles received, cumulative dose, duration of therapy, dose omissions, dose reductions, dose delays, and dose intensity will be summarized for all treated patients by cohort.

10.3.4 Interim Analyses

Interim analyses will be conducted regularly to evaluate closing enrollment early due to futility. For each cohort, the first futility interim analysis will be conducted after approximately 20 patients have been treated and completed ≥ 2 cycles or have discontinued before the first post-baseline tumor assessment. Although confirmation of response is not required to complete the interim analysis, the interim analysis may be potentially delayed to obtain confirmation of response. The futility rule is based on the posterior probability of activity via a Bayesian model. A cohort will be closed if the posterior probability is less than the prespecified futility threshold (e.g., 20% probability that ORR exceeds the prespecified threshold of activity). Borrowing of information across cohorts may be allowed, and the strength of borrowing may depend on the similarity among the cohorts. The prior distribution of response rate used in the model ~~will be~~ may be derived from the ongoing NCI-sponsored Phase 2 Study E001 (NCT02203513). The futility rules for each cohort are described as follows (ORR of 25% and 15% are considered the threshold of activity for Cohorts 1 – 3 and 4, respectively):

- Cohorts 1 to 3 (platinum-resistant): $\Pr(\text{ORR} > 25\%) < 20\%$
- Cohort 4 (platinum-refractory): $\Pr(\text{ORR} > 15\%) < 20\%$.

It is planned that enrollment can continue while interim analyses are conducted, but the sponsor may decide to pause the enrollment, if necessary. For the cohorts that can continue after the evaluation of the approximately first 20 patients, subsequent interim analyses will occur after approximately every 20 additional patients. The interval between interim analyses may be adjusted if deemed appropriate based on enrollment rates and available data. At each subsequent interim for each cohort, the posterior probability of response rate will be updated based on the available data and a higher futility threshold for the posterior probability may be adopted if deemed appropriate by the sponsor (~~e.g., 40% probability ORR exceeds the prespecified threshold of activity~~).

Leo Document ID = dff0e9fc-5663-410a-a5b6-e796458f5426

Approver: PPD

Approval Date & Time: 17-Sep-2018 14:05:08 GMT

Signature meaning: Approved

## Prexasertib (LY2606368) Ovarian Cancer

This study is a multicenter, nonrandomized, parallel cohort, Phase 2 study in patients with high-grade serous ovarian, primary peritoneal, or fallopian tube cancer. Patients will be assigned to cohorts based on their *BRCA* status and response to the platinum-based chemotherapy.

Eli Lilly and Company  
Indianapolis, Indiana USA 46285  
Protocol I4D-MC-JTJN  
Phase 2

Statistical Analysis Plan Version 1 electronically signed and approved by Lilly on date provided below.

Approval Date: 02-Apr-2018 GMT

**Revision History**

SAP Version 1 was approved prior to the first patient visit.

### 3. Study Objectives

Table JTJN.4.1 shows the objectives and endpoints of the study.

**Table JTJN.4.1. Objectives and Endpoints**

Objectives	Endpoints
Primary	
To estimate the ORR for each cohort	
 
• ORR: proportion of all enrolled patients who achieve a best overall response of PR+CR as determined per RECIST version 1.1.
 

Secondary	
To characterize the safety and toxicity profile of prexasertib	
 
• The safety endpoints evaluated will include but are not limited to the following: AEs, SAEs, clinical laboratory tests, ECGs vital signs, and physical examinations
 

To characterize the PK of prexasertib	
 
• Prexasertib concentrations in plasma
 

To estimate secondary efficacy measures including DCR, DoR, CA-125 response, PFS, OS	
 
• DCR: proportion of patients who achieve a best overall response of CR, PR and SD (for at least 4 months) as determined per RECIST version 1.1.
 
• DoR: time from the date measurement criteria for CR or PR (whichever is first recorded) are first met until the first date of documented PD, per RECIST 1.1 criteria, or the date of death from any cause in the absence of documented PD.
 
• CA-125 response: at least a 50% reduction in CA-125 levels from a pretreatment sample that is at least twice the upper limit of the reference range and obtained within 2 weeks before starting the treatment, with confirmation after 4 weeks according to GCIG criteria.
 
• PFS: time from enrollment until the first radiographic documentation (as assessed by the investigator) of progression or death from any cause in the absence of documented PD
 
• OS: time from enrollment until death from any cause
 

Tertiary/Exploratory	
To assess the relationship between biomarkers, prexasertib exposure (PK), and clinical outcomes	
 
• Biomarker research assessed from blood or tissue samples, unless precluded by local regulations
 
• Plasma concentration of prexasertib
 
• Clinical outcomes data
 

To evaluate the patient-reported outcomes using NCCN-FACT-FOSI 18 and Worst Pain NRS	
 
• Change from baseline
 
• Time to progression
 
• Association between time to pain progression and analgesic consumption
 
• Association between time to progression and select efficacy outcomes
 

Abbreviations: AEs = adverse events; CR = complete response; DCR = disease control rate; DoR = duration of response; ECG = electrocardiogram; GCIG = Gynecologic Cancer InterGroup; NFOSI-18 = National Comprehensive Cancer Network – Functional Assessment of Cancer Therapy – Ovarian Symptom Index-18; NRS = numeric rating scale; ORR = overall response rate; OS = overall survival; PD = progressive disease; PFS = progression-free survival; PK = pharmacokinetics; PR = partial response; RECIST = Response Evaluation Criteria In Solid Tumors version 1.1 (Eisenhauer et al. 2009); SAEs = serious adverse events; SD = stable disease.

## 4. Study Design

### 4.1. Summary of Study Design

Study I4D-MC-JTJN is a multicenter, nonrandomized, parallel cohort, Phase 2 study in approximately up to 180 patients with high-grade serous ovarian, primary peritoneal, or fallopian tube cancer. Patients will be assigned to the following cohorts:

- Cohort 1: Platinum-resistant, *BRCA* negative, and received  $\geq 3$  lines of prior therapy
- Cohort 2: Platinum-resistant, *BRCA* negative, and received  $< 3$  lines of prior therapy
- Cohort 3: Platinum-resistant, *BRCA* positive, there is no restriction on number of lines of prior therapy, but must have received prior PARP inhibitor
- Cohort 4: Platinum-refractory, *BRCA* positive or negative, no restrictions on number of lines of prior therapy

The study employs a Bayesian adaptive design that may close enrollment in specific cohorts early based on the interim analysis results during the course of the trial. The study will initially enroll approximately 20 patients to each cohort and then a Bayesian model will be used to evaluate the posterior probability of activity for each cohort. A cohort will be closed if the posterior probability of activity is  $< 20\%$ . Subsequent interim analyses will be done to further evaluate the posterior probability of activity after additional patients are enrolled to each cohort.

### 4.2. Determination of Sample Size

The maximum total sample size of this study is estimated to be approximately 180 patients. For each of the 4 cohorts, the minimum sample size is approximately 20 patients. The sample size for each cohort will be dependent on the outcomes of the interim analyses. As cohorts are halted, new eligible patients will be allocated to the enrolling cohorts. As a result, the maximum sample size of a single cohort is approximately 120 patients (e.g., if enrollment to all but one of the cohorts is stopped after the first interim analysis). The posterior credible intervals of ORR when the observed ORR is in the range of 0-35% are summarized in [Table JTJN.5.1](#). For illustrative purpose, the study drug will be considered active if  $ORR > 25\%$  and the uniform prior beta (1,1) is assumed in the Bayesian model. With the minimum sample size of  $N=20$ , the posterior probability of ORR exceeding 25% is  $< 20\%$  if the upper bound of 60% credible interval is  $< 25\%$ . With the maximum sample size of  $N=120$ , the posterior probability of ORR exceeding 25% is  $> 80\%$  if the lower bound of 60% credible interval is  $> 25\%$ .

The study efficacy may be monitored on an ongoing basis. The decision to close a cohort earlier may be made if results suggest the posterior probability of ORR exceeding the prespecified threshold of activity is well below 20%. The evaluation of the posterior probability of activity may occur before 20 patients are enrolled. For example, if the target response rate is 25%, under the uniform prior beta (1,1), the posterior probability that ORR is greater than 25% is only 13.3% if 0 response is observed out of 6 patients. If the target response rate is 15%, under the same prior, the posterior probability that ORR is greater than 15% is only 16.7% if 0 response is observed out of 10 patients.

**Table JTJN.5.1. Observed ORR and 60% Credible Interval**

N=20			N=120		
Number of Responders	Observed ORR	60% Credible Interval	Number of Responders	Observed ORR	60% Credible Interval
0	0%	1.1%-7.4%	0	0%	0.2%-1.3%
1	5%	3.9%-13.6%	6	5%	3.9%-7.4%
2	10%	7.4%-19.3%	12	10%	8.3%-12.9%
3	15%	11.1%-24.7%	18	15%	12.8%-18.3%
4	20%	15.1%-29.9%	24	20%	17.4%-23.5%
5	25%	19.1%-35.0%	30	25%	22.1-28.7%
6	30%	23.3%-40.0%	36	30%	26.8%-33.8%
7	35%	27.6%-44.9%	42	35%	31.6%-38.9%

Abbreviations: ORR = overall response rate.

## 5. A Priori Statistical Methods

### 5.1. General Considerations

Statistical analysis of this study will be the responsibility of Lilly. The interpretation of study results will be the responsibility of the Lilly clinical research physician (CRP) / clinical research scientist (CRS) and the statistician. The Lilly CRP/CRS and the statistician will also be responsible for the appropriate conduct of an internal review process for both the final study report and any study-related material to be authorized for publication.

The primary analysis of the primary endpoint of overall response rate (ORR) will be performed when all enrolled patients have completed  $\geq 2$  months of follow-up and/or investigator-assessed best response assessments have been completed for all patients. All secondary endpoints will be evaluated at this time. Additional updated analyses of efficacy (including but not limited to time-to-event variables) and safety (including but not limited to adverse events) may be conducted at later times (approximately 10-18 months after last patient is enrolled) if deemed appropriate by the sponsor.

All confidence intervals (CIs) will be given at a 2-sided 95%, unless otherwise stated.

Unless otherwise specified, baseline for the time-to-event endpoints will be the date of enrollment (the date of assigning patients to a cohort) and baseline for the safety analysis will be the last assessable baseline prior to the dose administration.

Any change to the data analysis methods described in the protocol/SAP will require an amendment ONLY if it changes a principal feature of the protocol/SAP. Any other change to the data analysis methods described in the protocol/SAP, and the justification for making the change, will be described in the clinical study report. Additional exploratory analyses will be conducted as deemed appropriate.

### 5.2. Populations

The following analysis sets will be defined for this study:

**Intent-to-Treat (ITT) population:** will include all enrolled patients (i.e., patients have been assigned to a cohort). The ITT population will be used for all baseline, efficacy and PRO analyses.

**Per-Protocol population:** will include all treated patients who do not have any major protocol violations that could potentially affect the efficacy conclusions. This population will be used for efficacy and PRO sensitivity analyses.

**Safety population:** will include all enrolled patients who have received  $\geq 1$  dose of prexasertib, regardless of their eligibility for the study. This population will be used for all dosing/exposure, and safety analyses.

**Pharmacokinetic population:** will include all enrolled patients who have received  $\geq 1$  full dose of prexasertib and have baseline and  $\geq 1$  postbaseline evaluable PK sample.

**Biomarker population:** will include all enrolled patients from whom a valid assay result has been obtained.

### 5.3. Handling of Dropouts or Missing Data

Missing data, except dates, will not be imputed. Historical data such as historical diagnosis, historical illness, pre-existing conditions and prior therapies should be collected in a sufficiently informative way. For example, in order to be considered as historical illness, events occurring in the same year as study entry should have at least a known month and year for the end date, while events occurring in previous years should have at least a known year for the end date. When dates need to be imputed, missing days will be replaced with 15th of the month and missing day/month with 01 JULY.

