**Table JTJN.6.1. PFS events/Censoring Scheme**

Situationa	Event/Censor	Date of Event or Censor
Tumor progression or death	Event	Earliest date of PD or death
No tumor progression and no death	Censored	Date of last adequate radiological assessment or date of randomization (whichever is later) b
Unless		
No baseline radiological tumor assessment available	Censored	Date of enrollment
No adequate postbaseline radiological tumor assessment available and death reported after missing 2 scan intervals following randomization b,c	Censored	Date of enrollment
Tumor progression or death documented immediately after missing 2 or more scan intervals following last adequate radiological tumor assessment or enrollment (whichever is later) b,c	Censored	Date of last adequate radiological assessment or date of enrollment (whichever is later) b
New anticancer therapy started before tumor progression or death	Censored	Date of last adequate radiological assessment prior to the start of new anticancer therapy or date of enrollment(whichever is later) b

Abbreviations: CR = complete response; PD = progressive disease; PFS = progression-free survival; PR = partial response; SD = stable disease.

- a Symptomatic deterioration (that is, symptomatic progression that is not radiologically confirmed) will not be considered as tumor progression.
- b Adequate radiological tumor assessment refers to an assessment with one of the following responses: CR, PR, SD, or PD.
- c 2 scan intervals = 4 months.

**Duration of response (DoR)** is defined as the time from the date measurement criteria for CR or PR (whichever is first recorded) are first met until the first radiographic documentation of progression or death from any cause in the absence of PD. The analysis is for confirmed responders only. Median duration of response will be estimated using the KM method. The DoR will be censored according to the same rules as PFS.

**Overall survival (OS)** is defined as the time from the date of enrollment until death from any cause. If the patient is alive, lost to follow-up or withdrawn from study at the time of data analysis, OS data will be censored on the last date the patient is known to be alive. Overall survival curves, median overall survival, and survival rates at 6 months intervals up to 24 months with 95% CI for each cohort will be estimated using the KM method.

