### **5.13.2. Adverse Events**

Adverse event (AE) verbatim terms will be provided by the investigators and then will be mapped by Lilly or its designee to corresponding terminology within the Medical Dictionary for Regulatory Activities (MedDRA) Lower Level term (LLT) dictionary. The investigator will use Common Terminology Criteria for Adverse Events (CTCAE) version 4.0 (NCI 2009) to assign AE severity grades.

Pre-existing conditions are defined as AEs that begin but do not resolve prior to the first dose of study drug in each study period. Pre-existing conditions will be presented by patient and can be combined with the listing of AE, so that the history of the pre-existing conditions/AEs can be traced.

A treatment emergent adverse event (TEAE) is defined as any AE that begins on or after the day of first dose in the reporting study period or any pre-existing condition that increases in CTCAE grade on or after the day of first dose in the reporting study period. The MedDRA LLT will be used in the treatment-emergent computation.

The number of patients who experienced a TEAE, or TEAE possibly related to study drug, will be summarized. Treatment-emergent adverse events will be summarized by SOC, by Preferred Term (PT) of decreasing frequency within SOC, and by maximum CTCAE grade and grade categories (any, Grade 3 or higher).

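### SAP 5.3 imputes partial dates as the 15th or 01 July without bounding them by known dates, so an imputed date can contradict a recorded one

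*SAP*

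**What the plan says.** SAP 5.3 opens with "Missing data, except dates, will not be imputed". It closes with the rule itself: "When dates need to be imputed, missing days will be replaced with" day 15 of the known month. Where only the year is known, the rule fills "missing day/month with 01 JULY". The only requirement on how complete a date must be is an example about historical illness: "events occurring in the same year as study entry should have at least a known month and year for the end date". It does not reach AE onset, death or the start of later therapy. Neither document limits an imputed date by first dose, enrollment, progression, last contact or death.

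Two classifications depend on date order:

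- **TEAE status (SAP 5.13.2).** A TEAE is "any AE that begins on or after the day of first dose in the reporting study period". A condition already present before first dose qualifies only if its CTCAE grade worsens from that day on.
- **PFS status (SAP Table JTJN.6.1).** The row "New anticancer therapy started before tumor progression or death" makes the observation censored at the last adequate scan before that therapy. SAP 5.9.1 applies the same rules to DoR.

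**The concern.** An imputation rule should not produce a date that contradicts one already on record. This one can, in three ways:

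- **AE onset.** First dose 20 June, true onset 25 June, day missing: the imputed onset is 15 June. The event now looks pre-dose. If unresolved at first dose it meets the SAP's definition of a pre-existing condition and counts as a TEAE only if its grade rises. A non-serious event lost this way also leaves the registry table of other AEs, which requires TEAE status (SAP 5.17).
- **New therapy.** Progression 20 March, therapy 25 March, day missing: the imputed start is 15 March. An observed progression becomes a censored observation.
- **Death.** A month-only or year-only death date can fall before the last contact. Partial death dates are plausible, because Protocol Table JTJN.3 allows survival follow-up by telephone about every 90 days and Protocol 8.3 allows searches of public sources.

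Cohorts may be as small as about 20 patients (Protocol 5.2), so one reclassified event is 1/20 = 5% of a cohort.

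**Working it through.** The plan gives no figure on this point to reproduce. The check applies the stated rule to every calendar day of a 365-day year and counts how often the imputed date falls before a known earlier date.

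**Assumptions not in the documents:** calendar days uniform; AE onset uniform over 28 or 112 days from first dose (counting the dose day); new therapy uniform over 1–28 or 1–56 days after progression; death uniform over 1–112 or 1–122 days after the last scan (two readings of the SAP's 4-month limit). Every share is conditional on the date being partial.

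**1. AE onset, day missing.** The imputed 15th precedes first dose when first dose is on day 16 or later and onset is in the same month. Day/onset pairs that qualify: 136 in a 31-day month (16+15+…+1), 120 in a 30-day month, 91 in February. Total = 7×136 + 4×120 + 91 = 1,523.
- Onset within 28 days: 1,523/(365×28) = 14.9%.
- Onset within 112 days: 1,523/(365×112) = 3.7%.

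**2. AE onset, day and month missing.** 01 July precedes first dose when first dose is after 1 July (183 days) and onset is in the same year.
- 28 days: (156×28 + 378)/10,220 = 46.4%.
- 112 days: (72×112 + 6,216)/40,880 = 34.9%.

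**3. New therapy after progression, day missing.** The logic is that of step 1, with therapy at least one day after progression: 7×120 + 4×105 + 78 = 1,338.
- 1–28 days: 1,338/10,220 = 13.1%.
- 1–56 days: 1,338/20,440 = 6.5%.
- As a variant, 30-day months and a lag of 0–28 days: 120/870 = 13.8%, about 14%.

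**4. New therapy, day and month missing.**
- 1–28 days: (155×28 + 378)/10,220 = 46.2%.
- 1–56 days: (127×56 + 1,540)/20,440 = 42.3%.

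**5. Death placed before the last scan, a date on which the patient was alive.**
- Day missing: 1,338/40,880 = 3.3% (112 days) or 1,338/44,530 = 3.0% (122 days).
- Day and month missing: 14,168/40,880 = 34.7% or 14,823/44,530 = 33.3%.

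**6. Errors the other way, 30-day months.**
- Same-month AEs truly before first dose that become TEAEs: 105/435 = 24%. The matching share of same-month on-treatment AEs moved to before first dose is 120/465 = 26%.
- Therapies truly begun 1–28 days before progression that are imputed on or after it, so that an event is wrongly kept: 105/840 = 12.5%, against about 14% in step 3.

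**7. Effect of a first-dose bound.** If an onset whose known month (or year) contains first dose is set no earlier than first dose, the shares in steps 1 and 2 fall to 0%.

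**The case against.** **Direction.** A reader might infer that the rule systematically loses TEAEs and lengthens PFS and DoR by censoring patients who progress and switch. Step 6 shows why the documents do not support that. AEs are recorded from consent (Protocol 9.2.1), so true pre-dose events exist and can become false TEAEs at a similar rate; therapy that truly came first can be placed after progression. The net effect depends on how many records lie on each side, which the plan does not give. This objection stands in full.

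**Size.** Shares as high as 26% to 50% for AEs can be derived, but only among day-missing AEs that truly began in the month of first dose. A share of 27% for therapy starts needs every switch to fall within 0–14 days of progression; at 7–21 days it is 36/450 = 8%. The documents support neither lag. Dosing visits every 14 days, AE collection throughout and computer edit checks on CRF data should also make partial AE dates uncommon.

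**Scope.** The rule closes a paragraph mostly about historical data, and its opening clause does not say which dates need imputing. It could be read as limited to history. But the section covers dropouts and missing data in general and exempts dates without qualification. If the narrow reading is right, AE, therapy and death dates have no rule at all, so text is needed either way.

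**Consequence.** ORR and the futility rules do not use these dates. SAEs are tabulated separately and enter the registry summary whatever their TEAE status. Laboratory shift tables also capture hematologic toxicity. PFS, DoR and OS are descriptive Kaplan-Meier estimates per cohort. This holds the severity down but does not justify impossible date orders in safety tables and secondary endpoints.

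**Conclusion.** The point holds as a minor one. Applied as written, SAP 5.3 can put an on-treatment AE before first dose, a death before the last date known alive, or a new therapy before a progression that preceded it. Under uniform-date assumptions the misordered share is about 3.7% to 14.9% of day-missing on-treatment AEs and about 6.5% to 14% of day-missing therapy starts after progression, rising to about 35% to 46% for both when the month is also missing. The number of patients affected cannot be stated, because the frequency of partial dates is not given; it may be close to zero. The documents do not show a net lengthening of PFS or DoR, or a net loss of TEAEs.

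**What to change.** State in SAP 5.3 which dates the rule covers, and that the 15th/01 July values apply only within known bounds:

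- **(a) AE onset.** Where the known month and year (or year alone) contain the first-dose date, set onset no earlier than first dose, unless the event is recorded as pre-existing or other recorded data show that it began or ended before first dose.
- **(b) Death.** The imputed date is later than the last date known alive.
- **(c) New anticancer therapy.** The imputed start is no earlier than the last study dose. This follows Protocol 8.1, which has prexasertib stopped before a new agent is introduced. Radiotherapy that Protocol 7.7 allows during study treatment would need to be excepted.

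Bound (c) does not settle every case: therapy can still be imputed between the last dose and a progression in the same period. For these, declare one convention, for example that therapy is taken as not before progression unless recorded data show otherwise, and list the patients affected.

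The cost is a few sentences and routine programming. Two choices are not neutral and should be declared: (a) resolves unclear AEs toward treatment-emergent, and the therapy convention resolves unclear cases toward a PFS or DoR event.
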